#### **Startle Probe Trial Composition: Slides (stimulus materials) & Instrumentation**

After completing the questionnaires (20 minutes), EMG electrodes will be attached around the participant's left orbicularis oculi region. A Biopac photoelectric sensor (plethysmograph) will also be placed over the participant's left index finger to monitor concurrent changes in heart rate and two mini-electrodes will be placed adjacently on the left hypothenar eminence to measure skin conductance. As shown in **Figure 7**, participants will be asked to rest quietly, while seated in a comfortable recliner, for a 15-minute baseline period. The subject will be told that a series of slides will be presented and that each slide should be viewed the entire time it is on the screen. In addition, the subject will be told that occasional noises may be heard over the headphones and can be ignored. Then one trial block consisting of 48 slides will be presented using procedures similar to those listed in the preliminary studies. Each slide will be presented for 6s, followed by a randomly determined interslide interval, 10 to 20 seconds in duration. The valence slides were selected from the International Affective Picture System (IAPS) (Center for the Study of Emotion and Attention, 1995) and are the same as used in our preliminary studies. These slides have been used in many previous startle probe experiments and have been standardized for valence and arousal (e.g.,). The smoking cue slides (lit cigarette, ash tray, people smoking, etc.) were developed in our laboratory for our preliminary study and will also be used here. The slides will be equally divided among the three valence categories and the smoking cues. Although the same slides will be used in each session, they will be counterbalanced across sessions so that subjects will see pictures from each category equally often in each position. Counterbalancing for slide order will be arranged so that, across subjects, each slide will be associated with a startle probe equally often. Using a computer controlled visual analog scale (electronic slider), participants will be asked to rate their current mood (e.g., interested, distressed, nervous, alert, tired, upset, etc.) and craving (none-very strong) following one out every fourth slide within each valence.

Startle probes and picture stimuli will be controlled and digitally presented with E-Prime software (Psychology Tools, Inc.). Picture stimuli will be projected onto a 3 x 5 foot white screen with an image size of 20 x 30 inches. Participants will sit approximately six feet from the viewing screen. The acoustic startle stimulus will consist of a 50-ms presentation of white noise with instantaneous rise time. The noise burst will be presented over matched (left and right) Telephonics TDH-49 headphones at an intensity of 100 dB. A startle probe will be presented during 32 of the 48 slides at a random time of 2-5 seconds after slide onset, such that a probe will be presented during 8 of the 12 slides within each valence condition. To enhance unpredictability of the startle presentation, startle probes will also be presented during 12 randomly selected inter-slide intervals (ITIs). Responses to startle probes given during the ITIs will be used as a control measure to assess startle responding in absence of emotional stimuli.

### Physiological Recording and Data Reduction

For eye blink recordings, the electromyogram (EMG) from the orbicularis oculi region under the left eye will be amplified with a bioamplifier (Biopac, Inc.) using a bandpass filter of 90-1K Hz and contour-following integrator with a time constant of 125 ms. To enhance recording sensitivity during the blink response, the EMG signal will be digitized at 1000 Hz from 50 ms before until 250 ms after acoustic startle probes. The Biopac MP100 data acquisition software permits real time scoring of each blink for peak and latency. Trials with clear movement artifact or excessive baseline activity will be rejected and trials with no blink will be scored as 0 magnitude.

As a concurrent measure of autonomic arousal, we will monitor heart rate and skin conductance using Biopac MP100 physiological monitoring system and data acquisition software. Previous studies suggest that heart rate deceleration is marked during negative picture viewing. In contrast, skin conductance responses increase with arousal level of the stimuli but are enhanced for both positive and negative events, in comparison to neutral slides. Heart rate data will be recorded continuously throughout the session and edited to correct for any missed or double triggered intervals. It will then be transformed to averages for every half second, and the values during slides will be expressed as change scores deviated from a 1-s pre-slide baseline. The average of seconds 2-4 (6.5-s values) will be computed for a summary score to use in subsequent descriptive analysis. Skin conductance responses (SCRs) will be scored as the largest response between 0.9 and 4 s after slide onset. A log transformation ( $\log[\text{SCR} + 1]$ ) will be performed to normalize the distribution. The skin conductance amplifier will be calibrated prior to each session to record a range of 0-40  $\mu\text{S}$ . All raw data, analog signals and scoring transformations will be stored directly on a 900Hz computer interfaced with the physiological recording instruments. Real time display of EMG (startle probe) activity, HR, and SC will be implemented during the session using the corresponding software.

At the end of the fourth and final session, all 48 slides will be repeated in a free-viewing procedure. The subject will be asked to view each slide for as long as desired (to a maximum of 30 s), terminating with a button press. Viewing time will be recorded to the nearest millisecond. The subject will then rate the slide on affective dimensions (positive, negative) and arousal (low, high) using an interactive computer display. These ratings, along with HR and SCR measures will be used as a cross-validation of the slide's intended effect on emotional valence (negative/positive) and arousal (high).

### Participant Compensation

Participants will be paid \$300 for attending all laboratory sessions. Payments will be structured as follows: \$60 per completed laboratory session (\$240 total), \$20 bonus for remaining abstinent at each of the 3 post-baseline sessions[PCP17]. In addition, following all laboratory sessions, participants will be paid \$5 per assessment for providing saliva samples to verify their abstinence.

### **Data Analysis**

Prior to inferential procedures, extensive descriptive analyses will be conducted of the startle magnitude scores. Standard descriptive statistics, including means, standard deviations, ranges, etc., will be computed together with ninety-five percent confidence intervals. Graphical methods, including boxplots and histograms, will also be employed to closely examine the distributions of the scores. If required, potential normalizing transformations will be explored. Bivariate associations between the scores and selected demographic variables including age, ethnicity, gender, initial cotinine, FTND score, depression history, baseline smoking level and other initial assessments will be evaluated Pearson's product moment correlation coefficients and ANOVA. Descriptive analyses of the distributions of the WSWS, CES-D, PANAS scores and other psychological assessments between groups and over the laboratory sessions will also be conducted. In addition, we will conduct descriptive and graphical analyses of the affective ratings for each slide obtained at the end all sessions. The end of study ratings from the free viewing situation will be plotted against startle magnitude as a check of the intended manipulation of valence. As described by Cuthbert, et al., startle magnitude will also be plotted against skin conductance levels to verify the arousal level (high) of the selected slides. Skin conductance has been shown to reliably track subjective arousal independent of valence. Similar descriptives will also be provided for the in-session mood and cravings ratings within each valence.

## Statistical Approach

**Table 3 Estimated Genotype & Allele Frequency**

Genotypes	Allele	Controls Freq. (%)	Smokers Freq. (%)
DRD2A	A1A1 or A1A2	25.9 a	42.6 g
DRD2B	A2A2	74.1	57.4
	B1B1 or B1B2	13.2 b	41.6 g
DRD4	B2B2	86.8	58.4
	SS	79 c	76 i
DAT	SL or LL	21	24
	9/9 or 9/10	55.8 d	46.7 d
SERT	10/10	44.2	53.3
	SS or SL	70.3 e	59.6 g
NET 1287G/A	LL	29.7	40.4
	GG	44 f	unknown
	GA	44	
	AA	12	

a= b= c= d= e= f= g= i=

Our primary analytic strategy involves the use a mixed model approach to examine the effects of the dependent variables (e.g., startle magnitude, time to rela9pse) across assessments. The mixed model approach provides a generalization to the classic linear regression model, using likelihood functions instead of least squares to estimate effects. The mixed model approach is ideally suited for analysis of repeated measures data in that it allows for more specific estimation of the correlation structure of the residuals, and more efficiently handles unbalanced designs and missing data, without excluding participants or imputing values. Fit statistics (e.g., Akaike's Information Criterion) will be evaluated for all models to ascertain the best fit of the correlation structure of the dataset. We use a computer program, PROC MIXED, (SAS Institute Inc, Cary, NC) to estimate and test the models. This procedure was used in our preliminary studies.

## Power

Analysis of the startle responses will be conducted using mixed model regression. The study design involves both between subject and within subject fixed effects and correlations due to repeated measures on the participants. Within subject fixed effects include Days (baseline, post quit days 2,5, 28) and slide valence (positive, negative, neutral, cigarette). Between subjects effects include Treatment (Placebo, Bupropion, Nortriptyline) and Genotype (e.g., A1/A1 or A1/A2 and A2/A2 for our main hypothesis, and others as described for secondary hypotheses). Because of the nonstandard design, power calculations were conducted using simulations in SAS (PROC MIXED). To simplify calculations, we

**Table 4 Effect Sizes & Corresponding Differences in Startle Magnitude (µVolts) For Comparisons Genotype Main Effects Varying Prevalence Rates of the At Risk Allele**

Prevalence of "at risk" allele	Model 1	Model 2	Model 3
.5	.15 (3)	.29 (20)	.29 (16)
.4	.16 (3)	.30 (20)	.30 (16)
.3	.17 (4)	.32 (22)	.31 (17)
.2	.20 (4)	.36 (25)	.35 (19)

assume that the response to the slides at each level of valence within session will be averaged. The repeated measures on each subject are associated with correlations between observations from the same subject across sessions, and between observations from the same subject within session. We estimated these correlations using data from our previous work. For the primary hypothesis described below, we will fit three models. The first (Model 1) will restrict analyses to positive, negative and cigarette, stimuli and use the score to the neutral stimuli as a covariate, the second (Model 2) will use data from all valences together, and the third (Model 3) will use all data but examine post-quit scores controlling for baseline scores. The within subject-between-session and within subject-within session correlations varied for each model in our preliminary work. For Model 1, we estimated the within subject-between session and within subject-within session correlations to be .03 and .45, respectively; for the Model 2 we estimated them to be .7 and .9, respectively, and for Model3, we estimated them to be .6 and .9, respectively.

We estimated power based on 354 subjects and a Type I error rate of 0.05. Power calculations were repeated for each of the three models. For Hypothesis 1, we estimated power for the group contrast between placebo and either bupropion or nortriptyline. A sample size of 354 subjects provides 80% power to detect effect sizes of .17, .32 and .30 standard deviations between these groups for Models 1, 2 and 3, respectively. Given the variability estimates in the raw startle magnitude scores we found by applying the three models to our previous work, these effect sizes translate into group differences in startle magnitude of 4, 22 and 16

µvolts, for Models 1,2 and 3, respectively. These values are well within the range observed in our preliminary studies where the overall difference between treatment and controls averaged 27 µvolts. This range also provides adequate power for detecting interactions with valence for any of the Models, as the range of differences between positive and negative valence between groups, is above 16 µvolts. For Hypothesis 2, we estimated power for the genotype comparisons across a range of possible prevalence for the “at risk” allele, among smokers. The expected allele frequency among smokers is shown in **Table 3**. Data from controls are provided for comparison but except in the case of the NET, are not considered in the power calculations. Power analyses for genotype effects are summarized in **Table 4**. Effect sizes are shown in standard deviation units. The corresponding difference in raw scores (µvolts) is shown in parentheses. Our major hypothesis involving genotype center on the DRD2, for which the A1 is the “at risk allele. As shown in **Table 3**, the expected frequency in our sample of smokers is above 40%. Effect sizes at this frequency and above vary from .15-.30, which corresponds to differences of 3-16 µvolts (see **Table 4**), for the three respective models. In our preliminary studies, the average difference in startle magnitude across all valences between A1 and A2 smokers who quit during the study was 26 µvolts, so we will have adequate power for these comparisons.

As described in the proposal, we will also examine other genotypes in exploratory analysis. For purposes of these comparisons, the “at risk” allele can be considered the GG allele of the NET, the L form of the DRD4 and the SERT, and the DAT 10/10. Data on the GG genotype of the NET are unknown for smokers so we used the control data from Zill. For all but the DRD4 the effect sizes and corresponding startle magnitudes are similar to the A1. For the DRD4 L allele the frequency is estimated at .24, corresponding to an effect size of .2-.35, and startle differences between 4-25 µvolts, across the three models. If the differences in startle magnitude are similar to those of the A1, we will still have adequate power to detect them, although this might be at the upper range for Model 2.

For the moderation of emotional reactivity during cessation by genotype, we again provide estimated power for the three models in **Table 5**. The effect estimates represent the difference in emotional reactivity

Prevalence of “at risk” allele	Model 1	Model 2	Model 3
.5	.32 (7)	.57 (39)	.57 (31)
.4	.34 (7)	.60 (41)	.59 (32)
.3	.37 (8)	.63 (43)	.62 (34)
.2	.42 (9)	.72 (49)	.70 (39)

between placebo and bupropion or nortriptyline between each of the two genotypes (e.g. A1 vs. A2). Our preliminary studies indicate that the difference between A1 participants in Quit group and A1 Controls (adjusting for baseline) ranged from 25-60µvolts over the two week of cessation period. Corresponding differences for A2s ranged from 25-2µvolts, and a significant interaction between genotype and Group (Quit vs. Control) was observed (i.e., A1 Quitters showed an elevated startle during cessation. Based on this estimate we will have

adequate power for detecting 2 way interactions with genotype, for all Models for our primary hypothesis (DRD2), and for our exploratory analysis of other genotypes, if similar results are observed. Our analytic strategy also calls for exploratory analysis of possible interactions between genotype abstinence status (Abstainers Relapsers Never Quitters), and treatment conditions. We expect all smokers in treatment to experience significant startle elevation as a consequence of abstinence or the reduced smoking observed among the Relapsers or Never Quitters, at least through the first week following cessation. If we estimate an overall abstinence rate at the end of treatment of 60%, and an at risk allele frequency of .43 (for the A1), that is the equivalent of a .26 “at risk” allele rate in **Table 5**. Therefore we should be able to detect differences in startle magnitude of 8-43µvolts, depending on the Model, for interactions between genotype, abstinence status and treatment. This range of startle activity also provides us with adequate power to detect interactions with valence, should they occur, as seen in our previous studies. Differences between A1 Relapsers, Never Quitters and Abstainers and A1 Controls across valences ranged from 7 to 40µvolts, across assessments. For A2s the range was more narrow (4-22µvolts). Thus, we should have we should have adequate power to detect interactions with valence, genotype, abstinence and treatment, should they occur.

Power for hypothesis 3 was estimated by dichotomizing emotional reactivity into two groups (high versus low), in order to make use of available standard power formulas. Our actual dependent measure will be a continuous measure of startle, which will offer a much finer gradation of the incremental differences in

abstinence attributable to startle activity. Nevertheless, these calculations should provide a conservative estimate of power. We used data from Hall to estimate abstinence rates for nortriptyline vs. placebo. Her data provides comparability to our study as she used an extensive behavioral counseling in both her placebo and nortriptyline treatment groups. The abstinence rates at the end of treatment, 3 months and 6 months follow-up for the nortriptyline group were 64%, 54% and 42%, and for the placebo group were 42%, 26% and 26%, yielding an average abstinence rate of 53%, 41% and 34% at the 3 respective time points. The bupropion/placebo abstinence rates of Hurt are somewhat lower than observed for nortriptyline, but were not used in these calculations because the behavioral treatment provided in that study was not as extensive as provided here. We believe our counseling intervention would increase rates similar to the nortriptyline group. However, the current study is not specifically powered to detect absolute differences in the abstinence rates between the two drug groups. The literature suggests that the rates for the two drug treated groups should be very similar to each other, assuming a similar level of behavioral counseling in both. However, we do expect to find differences in how smokers respond to each treatment in terms of emotional reactivity and genotype (Hypothesis 1 and 2) and that emotional reactivity predicts abstinence, independent of treatment (Hypothesis 3). If we assume an overall abstinence rate across all three groups at 6 months of approximately 40%, then 150 subjects per group (dichotomizing into high versus low) provides 80% power to detect differences in 6 month abstinence rates of 48% versus 32%, between high and low startle groups. If the overall abstinence rate is 30%, then we have 80% power to detect differences in the 6 months relapse rates of 37% versus 21%, and for overall abstinence of 20%, we have 80% power to detect differences of 26% versus 12%. These estimates are well within expected scenarios in the smoking cessation treatment literature. Thus, we have adequate power to differentiate startle responses across a range of abstinence rates.

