2. We hypothesize that smokers who are heterozygous (S/L) or homozygous (L/L) for the long form of the SERT gene are likely to experience less emotional reactivity in response to nortriptyline therapy vs. either bupropion or placebo.
3. Polymorphisms of the NET gene have not been extensively characterized in humans, and its relationship to antidepressant therapy has not yet been explored. We will evaluate the relationship of one of the currently known NET polymorphisms (1287G/A) and emotional reactivity during pharmacotherapy. As a working hypothesis we expect that smokers carrying the GG allele of the 1287G/A variant will show reduced emotional reactivity during nortriptyline therapy vs. bupropion or placebo, in comparison to their GA or AA counterparts, who are not expected to differ in response to the antidepressants.

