We have also completed some preliminary analyses involving some of the other genotypes, noting Group (Quit vs. Control) by genotype interactions for the SERT and DRD2 B1, similar to what we found for the A1. These analyses were not complete at the time of this writing but the results for the B1 are very similar to what we observed for the A1. In addition, an interesting finding was observed for the SERT. Smokers carrying the S/S form of the SERT show a significant decline in startle following abstinence, whereas those with the S/L or L/L polymorphism show a significant elevation. This meaning of this finding is unclear but suggests that like the A1s, S/L or S/L smokers are more likely to react to nicotine withdrawal with enhanced activation of avoidance pathways, but emotional reactivity of S/S smokers is reduced. In one of our recent studies we have found evidence of reduced nicotine dependence among S/S smokers. Individuals with this genotype are thought to have higher levels serotonin than those with S/L or S/S genotypes and this might reduce their dependence on nicotine (e.g., they may have less need to use nicotine for affect regulation). We did not find evidence in this preliminary analysis of higher levels of negative affect (PANAS) for Treatment S/S-S/L smokers, but this remains a question to be addressed as we accrue more participants.

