### DRD4

For the DRD4 dopamine receptor gene, genotyping will be performed as described by. Smokers will be classified as having long genotypes (L/L or S/L (i.e., homozygous or heterozygous for an allele  $\geq 6$  repeats) or short genotypes (S/S (both alleles < 6 repeats)).

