### SERT

Genotyping for the serotonin transporter (5-HTTLPR) will be carried out according to the methods of. Two variants of the 5-HTTLPR have been described: the long (L) variant (528 bp) and the short (S) variant (484 bp).

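### The power statement for SERT fits the Table 3 split (S carriers versus L/L), not the hypothesised grouping of S/L with L/L

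*Combined protocol and SAP*

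**What the plan says.** **Hypothesis.** Exploratory hypothesis 2 in A. Specific Aims, repeated under Secondary Analyses Involving Other Markers, concerns "smokers who are heterozygous (S/L) or homozygous (L/L) for the long form of the SERT gene", who are expected to be less reactive on nortriptyline than on bupropion or placebo. The complement of that group is S/S.

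**Preliminary data.** The startle result at the end of C. Preliminary Studies uses the same grouping. S/S smokers declined after abstinence, "whereas those with the S/L or L/L polymorphism show a significant elevation".

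**Frequencies.** Table 3, which the Power section names as the source of expected frequencies, gives SERT in smokers only as SS or SL 59.6% and LL 40.4%. It places the heterozygotes on the other side.

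**Genotyping.** The DRD4 paragraph fixes the analysis classes: "Smokers will be classified as having long genotypes (L/L or S/L" and so on. The DAT paragraph does likewise. The SERT paragraph says only "Two variants of the 5-HTTLPR have been described" and sets no classes.

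**Power.** The at-risk forms include "the L form of the DRD4 and the SERT". The text then states: "For all but the DRD4 the effect sizes and corresponding startle magnitudes are similar to the A1". DRD4, at .24, is given its own larger detectable effects and a caution for Model 2. A later sentence extends adequate power for two-way interactions to the other genotypes, on condition that similar results are seen.

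**The concern.** The SERT text and the SERT frequency row describe different two-group splits. The heterozygotes are a large group: if S/S is 10-20%, S/L is 59.6% minus that, or about 40-50% (roughly 140 to 176 of 354 people). Their placement decides how balanced the comparison is, and so how large a genotype effect must be to be detected.

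Secondary Analyses says that SERT will be tested for main effects and interactions as for the DRD2, which is a two-level term. For those tests the detectable effect now stated belongs to the Table 3 split. With no classes in the SERT genotyping paragraph, the split also remains open when the data are analysed.

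**Working it through.** **Inputs.** N = 354 and alpha .05 (Power). A1 carriers 42.6%, SERT L/L 40.4%, S carriers 59.6% (Table 3, smokers). Table 4, .4 row: .16/.30/.30 SD, or 3/20/16 µV, for Models 1/2/3; .2 row: .20/.36/.35 SD, or 4/25/19 µV. S/S in bladder cancer patients (Background, SERT subsection): 12.3% of current, 37.5% of never and 39.6% of former smokers.

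**1. Does the prevalence scaling reproduce the plan's tables?** At fixed N, alpha and power, the detectable difference between two groups is proportional to 1/√[p(1−p)]. From p = .4 to .2 this predicts √(.24/.16) = 1.22. Table 4 shows .20/.16 = 1.25, .36/.30 = 1.20 and .35/.30 = 1.17. Table 5 shows .42/.34 = 1.24, .72/.60 = 1.20 and .70/.59 = 1.19. The scaling follows the tables, though it is slightly steep for Models 2 and 3.

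**2. The plan's statement on its own split.** √[(.426 × .574)/(.404 × .596)] = √(.2445/.2408) = 1.008. For L/L versus S carriers, the comparison with the A1 is correct.

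**3. The S/S share (assumption).** Hardy-Weinberg from L/L: L = √.404 = .636, S = .364, S/S = .364² = .133, about 47 of 354. This is only approximate in a sample planned as racially mixed (Table 7). The 12.3% in current smokers is close to it. Working range: 10-20%.

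**4. The hypothesised split.** Ratio to the .4 row = √[.24/(p(1−p))]:

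| S/S share | Ratio | Main effect, Models 1/2/3 (µV) |
|---|---|---|
| .10 | 1.63 | 4.9 / 32.7 / 26.1 |
| .123 | 1.49 | 4.5 / 29.8 / 23.9 |
| .133 | 1.44 | 4.3 / 28.9 / 23.1 |
| .20 | 1.22 | 3.7 / 24.5 / 19.6 |

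For comparison, DRD4 at .24 has ratio √(.24/.1824) = 1.15. The Genotype × Group values in Table 5 would rise by about the same factors.

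**5. Against the plan's benchmark.** The Power section uses an observed A1/A2 difference of 26 µV. Models 1 and 3 stay at or below about 26 µV across the range. Model 2 exceeds it on this scaling if S/S is below about 17-18%. A closed-form check for Model 2 uses correlations .7 and .9: SD of a subject's mean = √[(1 + 3×.9 + 12×.7)/16] = .870. With 80% power and a two-sided test, the detectable effect is 2.80 × .870/√(354 × .1328 × .8672) = .38 SD, or about 26 µV at 22/.32 = 69 µV per SD. The same formula gives .264 SD at p = .4, where Table 4 prints .30. The absolute level is therefore uncertain and the Model 2 margin is small.

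**6. The hypothesised drug contrast.** Restricting to L carriers (.867 of the sample) multiplies the detectable difference by 1/√.867 = 1.074. The 4/22/16 µV given for Hypothesis 1 becomes 4.3/23.6/17.2 µV.

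**The case against.** The best reply has four parts.

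- **No SERT main effect is hypothesised.** The hypothesis is a drug contrast among L carriers, and that contrast barely changes (step 6). This stands, and it limits the point to the genotype main-effect and Genotype × Group tests that Secondary Analyses adds for every marker.
- **The sentence agrees with Table 3.** This also stands. It is not a calculation error; the table row does not match the hypothesis.
- **The S/S share is assumed.** True. At the 37.5-39.6% reported for never and former smokers the ratio to the .4 row is 1.00-1.01, and the statement would hold. But this trial enrols current smokers, for whom the only direct figure is 12.3%, and even at 20% the ratio is 1.22.
- **The ratios extrapolate below the last tabulated row.** They do, and they may be slightly steep. The direction is not in doubt.

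A reader might also take "higher levels of negative affect (PANAS) for Treatment S/S-S/L smokers" in C. Preliminary Studies as evidence that the investigators use both groupings. That paragraph contains other evident slips in genotype labels, so the phrase is not relied on here. The hypothesis, the analysis text and the startle result agree with one another. Table 3 is the outlier.

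**Conclusion.** The statement that SERT's detectable effects match those of the A1 holds for L/L versus S carriers and not for the grouping that the SERT hypothesis uses. If S/S is 10-20%, the detectable genotype effect under the hypothesised two-level split is roughly 1.2 to 1.6 times the .4-row value, about 1.44 times at 13%. Across that range S/S is rarer than the DRD4 group (.24), which the plan already excepts.

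A reader might infer that the SERT analysis is underpowered. The documents do not support that: they give no SERT effect in µV, Models 1 and 3 stay near or below the 26 µV benchmark, the Model 2 margin is small, and the interaction statement is already conditional. Nor is there any effect on the sample size or the DRD2 power. SERT is exploratory, so this is a minor correction. It rests on the assumed S/S share and on SERT being tested as a two-level factor.

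**What to change.** Keep the hypothesised grouping and bring the other places into line:

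1. In the SERT genotyping paragraph, state that SERT is analysed as S/S versus S/L or L/L.
2. Replace the SERT row of Table 3 with that split. Take the S/S share from the source data if available; otherwise give a labelled assumption with its range.
3. In the Power section, except SERT as well as DRD4 from the comparison with the A1.
4. Add one lower-prevalence row, about .13, to Tables 4 and 5 from the existing PROC MIXED simulation. The scaled values above are approximations and should not be entered in the plan.
5. Limit the interaction adequacy statement, as it applies to SERT, to what that row supports.

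Restating the hypothesis as L/L versus S carriers would also remove the mismatch. But it would fit the hypothesis to the power table and abandon the grouping of the preliminary startle result.

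The cost is one simulation rerun, a few lines of text, and a less favourable stated detectable effect for one exploratory marker. Sample size and primary analyses do not change.
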